### **6. STUDY PROCEDURES**

All patients must sign an informed consent prior to any study-specific procedures.

All assessments should be performed prior to dosing with IV study treatments unless otherwise indicated on the [Schedule of Activities](#) table. Assessments can be performed before or after daily IMRT during the CRT Phase. Acceptable time windows for performing each assessment are described in the column headers on the [Schedule of Activities](#) table where applicable.

## **6.1. Screening**

For screening procedures, see [Schedule of Activities](#) table as well as the Assessments section ([Section 7](#)).

Following informed consent, patients who complete screening assessments and are determined to be eligible may be registered use the IRT system. Screening assessments for eligibility MUST have already been completed before the patient is enrolled. To allow for additional flexibility in scheduling patient visit and procedures, Screening and Lead-in Day 1 procedures may be completed on the same day (see [Schedule of Activities](#) table).

## **6.2. Study Treatment Period**

For all on-treatment activities, see [Schedule of Activities](#) table as well as the Assessments section ([Section 7](#)).

### **6.2.1. Tumor Biospecimens**

#### **6.2.1.1. Mandatory Tumor Tissue**

An archival FFPE tumor tissue block from the most recent tumor resection or biopsy must be provided for all patients enrolled in the study and submitted to the Central Laboratory prior to randomization. If an FFPE tissue block cannot be provided, 15 unstained slides (10 minimum) will be acceptable. Tumor tissue from cytologic sampling (eg, fine-needle aspiration, including FFPE cell pellet material), is not adequate and should not be submitted.

#### **6.2.1.2. Optional Tumor Tissue – Lead-In Phase**

An optional tumor biopsy, to be collected 4 to 7 days following the single dose of avelumab in the Lead-in Phase, is requested for analysis of potential biomarkers of response. The de novo biopsy should be FFPE as per routine (see Study Manual), and the resulting FFPE tissue block(s) should be submitted to the Central Laboratory.

#### **6.2.1.3. De Novo Tumor Tissue – Maintenance Phase**

For patients who, during the course of the study, undergo a clinically-indicated tumor resection procedure, a tumor sample from the procedure should be collected and submitted to the Central Laboratory as an FFPE tissue block.

#### **6.2.1.4. De Novo Tumor Tissue – End of Treatment/Withdrawal**

A de novo (ie, fresh biopsy) tumor sample should also be collected at the End of Treatment/Withdrawal visit, unless clinically contraindicated or no tumor remains.

Tumor tissue from cytologic sampling (eg, fine needle aspiration, including FFPE cell pellet material) is not adequate and should not be submitted. The de novo biopsy should be FFPE as per routine (see Study Manual), and the resulting FFPE tissue block(s) should be submitted to the Central Laboratory.

### **6.3. End of Treatment, Short- and Long-term Follow-up Visits**

For End of Treatment, Follow-up, and Long-term Survival procedures, see [Schedule of Activities](#) table as well as Assessments section ([Section 7](#)).

In patients receiving investigational product up to the time of End of Treatment visit, additional safety follow-up visit will be scheduled for 30 days after the last dose received (Day 30  $\pm$  3) and a follow-up phone call will be performed 90 days after the last dose received (Day 90  $\pm$  3 [telephone contact]). If any concern arises during the follow-up phone call, the patient will be called in for a follow-up visit within 5 calendar days of the initial phone call for appropriate assessment (as per the investigator's medical judgement).

Patients continuing to experience treatment related toxicity following discontinuation of study treatment will continue to be followed at least every 4 weeks until resolution or determination, in the clinical judgment of the investigator, that no further improvement is expected.

### **6.4. Patient Withdrawal**

Patients may withdraw from the study at any time at their own request, or they may be withdrawn at the discretion of the investigator or sponsor for safety or behavioral reasons, or the inability of the patient to comply with the protocol-required schedule of study visits or procedures at a given study site.

Reasons for withdrawal of study treatment may include:

- Disease progression per modified RECIST v1.1;
- Global deterioration of health status requiring discontinuation;
- Unacceptable toxicity. If the unacceptable toxicity is clearly attributed to one of the investigational products, then withdrawal from study treatment may be considered, dependent upon the treatment and specific toxicity. If a patient cannot tolerate cisplatin, or has a toxicity-related treatment delay due to the radiation therapy, withdrawal from this study is neither required nor suggested;
- Pregnancy;
- Significant protocol violation (including radiation therapy protocol violations);
- Lost to follow-up;
- Patient refused further treatment;
- Study terminated by sponsor;
- Death.

Reasons for withdrawal from study follow-up may include:

- Study terminated by the Sponsor;
- Lost to follow-up;
- Refused further follow-up;
- Death.

If a patient does not return for a scheduled visit, every effort should be made to contact the patient. All attempts to contact the patient and information received during contact attempts must be documented in the patient's medical record. In any circumstance, every effort should be made to document patient outcome, if possible. The investigator should inquire about the reason for withdrawal, request that the patient return for a final visit, if applicable, and follow-up with the patient regarding any unresolved AEs.

If the patient refuses further visits, the patient should continue to be followed for survival unless the patient withdraws consent for disclosure of future information or for further contact. In this case, no further study specific evaluations should be performed, and no additional data should be collected. The sponsor may retain and continue to use any data collected before such withdrawal of consent.

## **7. ASSESSMENTS**

Every effort should be made to ensure that the protocol-required tests and procedures are completed as described. However, it is anticipated that from time to time there may be circumstances, outside of the control of the Investigator that may make it unfeasible to perform the test. In these cases the investigator will take all steps necessary to ensure the safety and well-being of the patient. When a protocol-required test cannot be performed, the investigator will document the reason for this and any corrective and preventive actions that he or she has taken to ensure that normal processes are adhered to as soon as possible. The study team will be informed of these incidents in a timely fashion.

### **7.1. Assessment of Progression**

For all suspected progression of disease that is detected clinically, but is not visible on radiographic imaging, direct imaging (ie, photographs) are required. This requirement is in addition to the requirement for pathologic confirmation of progression.

Tissue (pathologic) confirmation of disease is expected and required on this protocol for all local and regional lymph node suspected progression of disease. It is highly recommended that all new distant lesions suspicious for metastatic disease are also biopsied and pathologically confirmed. Good clinical judgment is expected to be utilized on biopsy ascertainment including, but not limited to, the situations below.

The following are expectations for biopsy ascertainment on a patient. If any of these conditions are met, it is expected that a biopsy will be performed, and the reason for biopsy and pathologic findings noted in the CRF. If a biopsy is not performed, clinical rationale must be entered into the CRF.

- New or significantly increased lesions on imaging or clinical exam;
- Mucosal ulceration;
- Suspicious mucosal changes;
- Suspicion of unresolved disease at the primary tumor location at the 12 week post CRT visit (primary treatment failure and a PD event if biopsy is positive);
- Significant enlargement, or newly enlarged, regional lymph nodes on clinical exam or imaging;
- Areas of PET-positive fludeoxyglucose (FDG)- uptake;
- Change of clinical findings on regional lymph node (neck) exam with new enlargement of a lymph node or group of nodes, or changes in character of lymph node group to palpation (eg, becoming harder or decreased mobility on physical exam - such as feeling attached to overlying skin, subcutaneous tissue or muscles, or underlying bone or muscle).

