#### **3.4. Surgical Salvage of Residual Disease after Completion of the CRT Phase**

[figure not shown]
Treatment of residual disease at the primary site will be determined by the investigator and the clinical situation (see [Figure 4](#)). If treatment at the primary site is necessary after completion of CRT, study treatment has failed and the patient will discontinue the study treatment. Surgical resection, re-irradiation, chemotherapy, or palliative care may be performed per institutional policy. If the primary site is cleared of residual disease yet residual disease at the cervical nodal basin is suggested by imaging/clinical evaluation, then selective neck dissection will be performed unless a cytologic sampling of the node is negative. Residual disease in the neck is not considered a treatment failure if surgical salvage is completed within 140 days of completion of CRT. A primary treatment neck dissection after completion of the CRT Phase will be defined as a neck dissection performed for residual disease and within 20 weeks (140 days) of completion of CRT. Patients who undergo such a primary treatment neck dissection will not be considered experiencing a disease progression event and remain on study treatment, regardless whether neck specimens are positive or negative.

Positive specimens removed within 140 days of completion of CRT will be considered part of the initial treatment plan and not considered failures of initial management; positive specimens upon neck dissection beyond 140 days will be considered regional failures. Such consolidation neck dissections after completion of the CRT Phase will encompass only the areas (typically only levels 2 and 3) initially involved in the side of the neck in question. The extent of neck dissections performed for nodal recurrence or nodal progression, and/or salvage of disease at the primary will be determined by the treating surgeon.

If a neck dissection is required, then the treating surgeon is required to contact the surgical Principal Investigator (PI) of this study, [name] prior to the surgery to discuss the clinical and radiologic findings as well as the planned surgery itself. Notes from the surgery, as well as the pathology report from the neck dissection, must also be submitted to [name] for review when they become available, but no later than 6 weeks following the procedure.

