### **9.3.1. Analysis of the Primary Endpoint**

PFS is defined as the time from the date of randomization to the date of the first documentation of objective PD per modified RECIST v1.1 or death due to any cause, whichever occurs first.

The following will be considered events in the analysis of PFS:

- Death due to any cause;

- Locoregional disease progression per RECIST v1.1 which is subsequently confirmed by pathology;
- Locoregional clinically detectable progression that is confirmed by pathology;
- Surgical removal (salvage) of primary tumor with tumor present on final pathology;
- Salvage neck dissection >20 weeks (140 days) after completion of SOC CRT with tumor present on final pathology;
- Metastatic (distant metastases) disease progression per RECIST v1.1.

For the primary analysis, PFS data will be censored on the date of the last adequate tumor assessment for patients who do not have an event (PD per modified RECIST v1.1 or death); the analysis will consider any PD per modified RECIST v1.1 or death as an event regardless of the number of prior missing tumor assessments or timing of the event with respect to initiation of anti-cancer therapy.

The primary analysis of PFS will be performed based on the FAS. A stratified log-rank test (1-sided) stratified by randomization stratification factors will be used at the interim and/or final analyses with the overall significance level preserved at 0.025 (1-sided). PFS times associated with each treatment arm will be summarized using the Kaplan-Meier method and displayed graphically where appropriate. CIs for the 25th, 50th, and 75th percentiles will be reported. The stratified Cox proportional hazards model will be fitted to compute the treatment hazard ratio and the corresponding 95% CI.

A sensitivity analysis for PFS will be performed using the methodology outlined for the primary analysis of PFS above but defining PD as per standard RECIST v1.1. Summary of discordance of PD (event and timing) as well as reasons for discordance between assessment of PFS per modified RECIST v1.1 and standard RECIST v1.1 will be provided for each treatment arm.

PFS based on modified RECIST v1.1 will also be evaluated based on the per-protocol analysis set as a sensitivity analysis using the methodology outlined for the primary analysis of PFS.

Other sensitivity analyses will be pre-specified in the SAP.

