### 6.1. Primary Endpoints

#### 6.1.1. Progression-free survival per modified RECIST v1.1

##### 6.1.1.1. Primary analysis

The following analyses will be based on the FAS using the strata assigned at randomization. PD below refers to PD by investigator assessment per modified RECIST v1.1. Tumor-related endpoints in this study will be based on RECIST v1.1 modified with respect to the definition of what constitutes PD as follows (Appendix 3 of the B9991016 protocol). Any of the following will constitute PD per modified RECIST v1.1:

- Locoregional disease progression per RECIST v1.1 which is subsequently confirmed by pathology. Pathologic confirmation of progression will verify that radiographic changes

represent true tumor progression and not radiation effects or non-malignant contrast enhancement;

- Locoregional clinically detectable progression that is confirmed by pathology;
- Surgical removal (salvage) of primary tumor with tumor present on final pathology;
- Salvage neck dissection >20 weeks (140 days) after completion of CRT with tumor present on final pathology;
- Metastatic (distant metastases) disease progression per RECIST v1.1. Confirmation of pathology is recommended unless medically contraindicated or lesion location too high risk for biopsy.

**Local failure** is defined as residual or recurrent viable tumor on pathologic evaluation from the site of original tumor location. Presence of tumor is required for declaration of a progression event which requires identification of viable tumor cells on final pathology. Tumor reappearing within the initial and immediately adjoining anatomical region of the primary will be considered local recurrence.

**Regional failure** is defined as residual or recurrent viable tumor on pathologic evaluation from the regional lymph node basins (eg, neck nodes). Presence of tumor is required for declaration of a progression event which requires identification of viable tumor cells on final pathology.

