**Distant metastatic disease** is defined as new tumor identified at a site distant from the head and neck anatomic region or draining lymph nodes. Biopsy of any presumed distant metastatic disease is strongly recommended. A solitary, speculated lung mass/nodule is a second primary neoplasm and is not a disease progression event unless proven otherwise by biopsy in a patient with a smoking history. Multiple lung nodules/masses are considered distant metastases from the index cancer and constitutes a disease progression event unless proven otherwise by biopsy.

Irradiation of the primary tumor and radiographically enlarged lymph nodes is considered part of the treatment under investigation in this clinical trial and therefore these target lesions remain evaluable lesions for response assessment.

It is expected that the status of the primary tumor is assessed thoroughly at the beginning of the surgical procedure before undertaking nodal dissection. Presence of persistent disease at the primary site, confirmed by frozen section will be considered disease progression.

Neck dissection parameters are described in Section 3.4 of the B9991016 protocol and will consist of a selective neck dissection unless a cytologic sampling of the nodes that appear enlarged is negative. Positive neck specimens removed within 140 days after completion of CRT will be considered part of the initial treatment plan and not considered as failures of initial management; positive specimens upon neck dissection beyond 140 days will be considered regional failures.

Progression-Free Survival (PFS) is defined as the time from the date of randomization to the date of the first documentation of PD or death due to any cause, whichever occurs first. For example, the date of first documentation of PD when there is locoregional PD per RECIST v1.1 which is subsequently confirmed by pathology, will be the date of the locoregional PD per RECIST v1.1 rather than the date of pathology confirmation.

PFS data will be censored on the date of the last adequate tumor assessment or clinical evaluation for patients who do not have an event (PD or death); the analysis will consider any PD or death as an event regardless of the number of prior missing tumor assessments or clinical evaluations or timing of the event with respect to initiation of subsequent anti-cancer therapy.

The censoring and event date options to be considered for the PFS and DR analysis are presented in Table 9.

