**Table 10. PFS Censoring Reasons and Hierarchy**

Hierarchy	Condition	Censoring Reason
1	No adequate baseline assessment AND no PD AND no death	No adequate baseline assessment
2	No event and [withdrawal of consent date $\geq$ date of randomization OR End of study (EOS) = Patient refused further follow-up]	Withdrawal of consent
3	No event and lost to follow-up in any disposition page	Lost to follow-up
4	No event and [EOS present OR disposition page for any epoch after screening says patient will not continue into any subsequent phase of the study] and no adequate post-baseline assessment	No adequate post-baseline assessment
5	No event and none of the conditions in the prior hierarchy are met	Ongoing without an event

The PFS time or censoring time and the reasons for censoring will also be presented in a patient listing.

Frequency (number and percentage) of patients with each subtype of PD will be presented by treatment arm. The subtype of PD is collected in the eCRF and includes the following:

- Locoregional PD per RECIST v1.1 with pathologic confirmation
- Locoregional clinically detectable progression with pathologic confirmation
- Surgical removal (salvage) of primary tumor with tumor present on final pathology
- Salvage neck dissection >20 weeks after completion of SOC CRT with tumor present on final pathology

- Metastatic (distant metastases) disease progression per RECIST v1.1.

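### Protocol 7.1 counts biopsy-proven residual primary disease as PD, but the listed PFS and LRF events, PD subtypes and PD date rule do not cover it when it is neither growing nor resected

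*Protocol*

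**What the plan says.** Protocol 7.1 lists situations in which a biopsy is expected. One is suspected unresolved disease at the primary tumor location at the 12-week post-CRT visit, which it labels "primary treatment failure and a PD event if biopsy is positive". Neither growth nor resection is required.

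Protocol 9.3.1 enumerates the PFS events. Apart from death and distant progression there are four locoregional items:
- an item based on RECIST measurement: "Locoregional disease progression per RECIST v1.1 which is subsequently confirmed by pathology";
- an item based on clinical findings: "Locoregional clinically detectable progression that is confirmed by pathology";
- a surgical item for the primary site: "Surgical removal (salvage) of primary tumor with tumor present on final pathology";
- an item for the neck, namely late salvage dissection (over 140 days after CRT) in which the specimen contains tumor.

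Protocol 3.3, Appendix 3 and SAP 6.1.1.1 carry the same PD bullets. After Table 10 the SAP says: "The subtype of PD is collected in the eCRF and includes the following". The five subtypes that follow are the same items. SAP 6.2.2.4 defines LRF by the four locoregional items.

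Below the bullets, Protocol 3.3, Appendix 3 and SAP 6.1.1.1 add narrative. Local failure "is defined as residual or recurrent viable tumor on pathologic evaluation from the site of original tumor location". They also say: "Presence of persistent disease at the primary site, confirmed by frozen section will be considered disease progression".

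Protocol 3.4 states: "If treatment at the primary site is necessary after completion of CRT, study treatment has failed". It foresees non-surgical as well as surgical management, so unresected cases can occur.

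On dating, Protocol 7.8 and SAP 6.1.1.1 place confirmed locoregional PD at the date of the evaluation that showed progression, not the date of pathology.

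**The concern.** PFS by investigator assessment is the primary endpoint and needs one definition. Section 7.1 and the narrative treat persistence of tumor at the primary site as failure. The lists that investigators and programmers work from are built on progression or surgical removal.

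A primary that shrank after CRT, is still biopsy-positive and is not resected falls between the two. Two sites with identical patients could record different PFS times. The secondary endpoint LRF, which should capture a proven failure at the primary site, does not name this case at all.

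**Working it through.** **Step 1. Apply the lists to one patient.** At 12 weeks post-CRT the primary is smaller than at baseline, the scan reads PR or SD, a biopsy shows viable tumor, and the primary is not resected.

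| Listed item | Met? |
|---|---|
| RECIST locoregional progression, confirmed by pathology | No. There is no growth over nadir and no new lesion |
| Clinically detectable progression, confirmed by pathology | Pathology yes; progression no on a literal reading, though a site might use this item |
| Surgical removal of the primary with tumor on pathology | No. Not resected |
| Neck dissection after 140 days with tumor | Not applicable |
| Distant progression | No |
| Protocol 7.1 | Yes, PD event |

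**Step 2. Does the narrative settle it?** Not fully.
- The local-failure text makes tumor presence a requirement for declaring a progression event. That is a necessary condition, not a statement that residual tumor alone is PD.
- Regional failure is defined in parallel wording that also includes residual tumor. Yet positive neck specimens within 140 days are expressly not failures. So a failure definition does not by itself create an event.
- The local-failure text asks for viable cells on final pathology. Protocol 3.3 and Appendix 3 mention biopsied as well as resected specimens. SAP 6.1.1.1 does not repeat that sentence, and no section says outright that a biopsy is final pathology.
- The frozen-section sentence follows one about assessing the primary at the start of a surgical procedure. It does not address a biopsy in a patient who is not operated on.

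**Step 3. Trace the two recordings.**
- Recorded under 7.1: event at about the 12-week visit, but with no date rule, because the rules refer to the evaluation that showed progression.
- Recorded under the lists: the PR or SD scan is an adequate assessment (SAP 5.2.11). The patient stays event-free until later PD or death, or is censored at the last adequate assessment (SAP Table 9). The next scheduled scan is 16 weeks later.
- LRF: the patient enters only through a later listed locoregional item or death.
- Sensitivity analyses: M2 to M4 keep the same PD definition. S0 uses standard RECIST, under which shrunken persistent disease is not PD. M1 censors at new anti-cancer therapy (SAP Table 12), which includes drug therapy and curative-intent radiation (SAP 5.2.6). A case not recorded as PD and then given such therapy is censored in M1.

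**Step 4. Reproduce the design figure.** Inputs from Protocol 9.1 and 9.6: HR 0.68, 1-sided alpha 0.025, power at least 90%, 289 events, interim at 217.
- Fixed design: 4 × (1.960 + 1.282)² / (ln 0.68)² = 283 events.
- Group-sequential, information fraction 217/289, O'Brien-Fleming-type spending: interim alpha 0.0097, z 2.338, final nominal p 0.022, power 90.2% at 289 events.

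The stated figures reproduce. Counting or not counting these cases does not change the 289-event requirement.

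**Step 5. Size the effect under assumption.** The documents give no rate, so the rates below are assumed. The simulation used 1,500 trials per row with 320 patients per arm, medians of 33 and 48.5 months, uniform accrual over 22 months and 15% dropout. The cutoff was 289 events and 24 months after the end of accrual. The test was unstratified at the final look only. Residual failure was placed at 1 + 7 + 12 = 20 weeks after randomization. If uncounted, the event is death a median of 6 or 10.1 months later, the range that Protocol 1.3 quotes for survival in recurrent disease. Both versions were computed on the same simulated trials.

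| Rate, Arm B / Arm A | Median to death (months) | HR counted → delayed | Power counted → delayed |
|---|---|---|---|
| 3% / 2% | 6 | 0.682 → 0.683 | 89.3% → 89.2% |
| 3% / 2% | 10.1 | 0.679 → 0.681 | 89.3% → 88.3% |
| 5% / 3.4% | 6 | 0.678 → 0.680 | 90.5% → 90.3% |
| 5% / 3.4% | 10.1 | 0.680 → 0.684 | 90.3% → 88.2% |
| 10% / 6.8% | 6 | 0.680 → 0.683 | 90.7% → 89.3% |
| 10% / 6.8% | 10.1 | 0.680 → 0.688 | 91.2% → 88.5% |
| 10% / 5% | 6 | 0.649 → 0.658 | 95.7% → 94.6% |
| 10% / 5% | 10.1 | 0.648 → 0.667 | 95.9% → 92.8% |
| 5% / 5% | 6 | 0.708 → 0.704 | 82.3% → 84.3% |
| 5% / 5% | 10.1 | 0.707 → 0.701 | 83.8% → 84.9% |

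Simulation error in each power figure is about 1 point. The largest HR shift is 0.667 − 0.648 = 0.019. The largest power change is 95.9 − 92.8 = 3.1 points.

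**The case against.** The best reply is that residual primary disease is already inside the endpoint. PFS is time to PD per modified RECIST, a term defined by the whole of Protocol 3.3 and Appendix 3. Those sections count residual viable tumor as local failure and mention biopsied specimens. The bullets open by saying that any of them constitutes PD, not that only they do. Nowhere is biopsy-positive residual primary disease called a non-event, whereas the neck exception is spelled out. A site could enter the case as clinically detectable progression. The eCRF itself is not in the documents, and the SAP's list may not be exhaustive. Biopsy reason and outcome are recorded and tabulated by lesion (SAP 6.2.2.2), so cases can be found. The trial is double-blind with the same assessment schedule in both arms.

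Most of this stands, and it limits the point. A reader might infer that the PFS definition simply omits residual primary failure, or that unresected cases stay event-free for good. The documents do not support either: the narrative includes residual tumor, and Protocol 9.3.1 counts any later PD or death regardless of intervening therapy.

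What the reply does not remove is the mismatch. SAP 6.2.2.4 defines LRF by its four items with no narrative to widen it. The date rules cover progression, not persistence. Using the clinical-progression item requires a site to call persistence progression.

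**Conclusion.** The point holds as an unreconciled conflict: Protocol 7.1 and the narrative on one side, the enumerated events, listed subtypes, LRF definition and date rule on the other. It should be fixed, but it does not undermine the design.

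The consequence for PFS is mainly a late event date, with censoring if follow-up ends first. For LRF, the patient is outside the definition as literally written until a listed item or death occurs. Under assumed rates of 2% to 10%, the PFS hazard ratio moves by at most about 0.02 and power by at most about 3 points. The direction depends on how cases split between arms: toward 1 when they are commoner in Arm B, away from 1 when the rates are equal. These figures rest on the assumed rates, the 20-week timing and the assumed time to death.

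A reader might multiply a rate by 640, divide by 289, and conclude that a large share of the events is at stake. That does not follow. The rate has no source in the documents, and the product counts patients whose status or date is ambiguous, not events lost.

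**What to change.** Reconcile Protocol 7.1, 3.3, 9.3.1 and Appendix 3, SAP 6.1.1.1 and 6.2.2.4, and the eCRF PD subtypes so that they state one rule. To match the intent of 7.1:
- add a PD item, an LRF item and an eCRF subtype for biopsy-positive residual tumor at the primary site at the 12-week post-CRT visit;
- state that a biopsy satisfies the pathology requirement;
- date the event at the assessment that prompted the biopsy, in line with the convention already used for confirmed locoregional PD.

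Keep the item to the 12-week visit. Extending it to later visits would widen the rule and would need a matching change in 7.1. If the sponsor instead intends that such cases are not events, 7.1 must say so.

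The cost is protocol and SAP wording plus one eCRF code. Protocol 7.1 already expects the biopsies and has their findings noted in the CRF. The sample size, event target and boundaries do not change.
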